Patients in Cohort 1 will receive either LY3298176 with titration regimen starting from 2.5 mg for Days 1 and 8 followed by 5 mg for Days 15 and 22, and 10 mg for Days 29, 36, 43, and 50, or corresponding volume-matched placebo. Patients in Cohort 2 will receive either LY3298176 with titration regimen starting from 5 mg for Days 1 and 8 followed by 10 mg for Days 15, 22, 29, and 36, and 15 mg for Days 43 and 50, or corresponding volume-matched placebo. Patients in Cohort 3 will receive either 5 mg LY3298176 or placebo for 8 weeks (Section 5.5). The planned highest dose or dosing regimen of Cohort 2 may be changed for the reason of tolerability (Section 7.4).

If the investigator decides not to up-titrate the dose level of IMP for individual patients in the titration regimen in Cohorts 1 or 2 for the reason of safety and/or tolerability, patients may keep current dose level to the planned last dose at Day 50 and will no longer be allowed up-titration during the treatment period. Down-titration is not allowed during the treatment period for any patients in Cohorts 1, 2, or 3.

Safety, as assessed by AEs, vital signs, 12-lead ECGs, concomitant medications, safety laboratory measurements, and medical assessments from at least 8 patients (to include at least 5 on LY3298176) up to Day 36 predose procedure of Cohort 1, will be reviewed by the sponsor and investigator before dose-escalation decision to Cohort 2 (Section 7.4.1).

Dosing will be staggered in Cohorts 1 and 2 so that an initial group of up to 6 patients receiving LY3298176 and 2 patients receiving placebo will be dosed. On Days 4 and 32 of Cohort 1 and on Days 4, 18, and 46 of Cohort 2, the investigator and Lilly clinical pharmacologist, clinical research physician (CRP), or clinical research scientist (CRS) will review available safety data from these patients, and if no relevant safety signals are noted, the remaining patients will be dosed. Patients in Cohort 3 will be dosed after evaluation of safety data of the initial staggered group of Cohort 2.

PK sampling and safety assessments, including AEs, concomitant medications, medical assessments, clinical laboratory tests, vital signs, and ECGs, will be performed according to the Schedule of Activities (Section 2).

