7.4.1. Dose Escalation

The dose escalation decision will be made on the basis of the safety data at the 10-mg dose level of Cohort 1 to proceed to Cohort 2. The safety data up to Day 36 (predose procedure) of Cohort 1 from at least 8 patients (to include at least 5 on LY3298176) will be reviewed.

Safety data will be the primary criteria for the dose escalation. In addition, if available at the time of dose-escalation decision, PK results may be used as supporting data for dose escalation. No dose decision can occur without prior discussion and agreement between the investigator and the Lilly clinical pharmacologist, CRP, or CRS.

Safety data, in particular AEs, SAEs, and adverse laboratory abnormalities, will be independently assessed by the investigator and will be considered related to the IMP unless there is clear evidence that the event is not related.

After review of these data, an agreement on the appropriate dose will be made by the investigator and sponsor for Cohort 2.

The planned dosing regimen of Cohort 2 may be changed to 2.5 mg for Days 1 and 8; followed by 5 mg for Days 15 and 22; and 8 mg for Days 29, 36, 43, and 50, or the corresponding volume-matched placebo before the first dose of Cohort 2 if the safety assessment for the dose-escalation decision indicates that the 10-mg dose of Cohort 1 is not well tolerated.

If any of the following scenarios occur, dosing at the current level and dose-escalation from Cohort 1 to Cohort 2 will be discontinued:

- 1) if a single patient experiences an SAE other than anticipated pharmacology of LY3298176 (for example, GI-related AEs [particularly nausea, vomiting, and diarrhea] or hypoglycemia)
- 2) two clinically significant events (CSEs) in each cohort that are related to LY3298176 administration, with the exception of anticipated pharmacology of LY3298176
- 3) if 50% or more of patients in a cohort experience a symptomatic hypoglycemic episode with plasma/serum glucose levels of ≤ 3.0 mmol/L [54 mg/dL])

- 4) if more than 4 patients in 1 cohort experience moderate treatment-related AEs that impair normal activities
- 5) if 2 or more patients experience an acute pancreatitis event ([Appendix 6](#))

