Samples from patients in each cohort will be tested for the development of treatment-emergent antidrug antibodies (TE-ADAs) against LY3298176. A blood sample will be collected at specific study visits according to the Schedule of Activities (Section 2). All samples for immunogenicity should be taken predose when applicable. To interpret the results of immunogenicity, a PK sample should be collected at the same time point as the immunogenicity sample. In the event of drug hypersensitivity reactions (immediate or nonimmediate), additional samples will be collected as close to the onset of the event as possible, at the resolution of the event, and 30 days after the event. Instructions for the collection and handling of blood samples will be provided by the sponsor. The actual date and 24-hour time period of each sampling will

All patients will have an ADA sample measured at early discontinuation or at the follow-up visit (Day 85) approximately 5 weeks after the last dose of LY3298176. A risk-based approach will be used to monitor patients who have clinically significant TE-ADAs at the last visit. Treatment-emergent ADAs are defined as those with a titer 2-fold (1 dilution) greater than the minimum required dilution if no ADAs were detected at baseline or those with a 4-fold (2 dilutions) increase in titer from baseline if ADAs were detected at baseline. Clinically significant TE-ADAs will be defined as any TE-ADA at the follow-up visit (Day 85) with:

- a high titer (≥ 1280) or an increasing titer from last measured value
- an association of the TE-ADA with a moderate to severe injection-site reaction or infusion-related reaction
- cross-reactive and/or neutralizing binding of an ADA with endogenous GLP-1 or GIP

Patients who have clinically significant TE-ADAs should be followed up with ADA testing every 3 months for up to approximately 1 year or until the ADA titers have returned to baseline ADA titer (defined as ADA titer within 2-fold of baseline), whichever occurs earlier. A PK sample may be collected at the follow-up immunogenicity assessment(s) if warranted and agreed upon between both the investigator and sponsor.

Every attempt should be made to contact patients for the follow-up immunogenicity assessment; however, if patients are unwilling or unable to return for the visit, this is not considered a protocol violation.

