Appendix 4. Clinically Significant Adverse Effects

The table below summarizes the type and severity of symptoms, clinical signs, and clinical laboratory findings that may qualify as a clinically significant event. These are intended as a guideline to the investigator(s), not as a set of absolute criteria. The underlying principle is to define a level of moderate to severe abnormality in safety findings that could cause harm to health and would preclude further dosing of a patient/subject who experiences this effect. Safety parameters not included in this table may be interpreted in a similar fashion according to investigator judgment.

Clinically Significant Adverse Effects

Parameter	CSE level
Symptoms	
Severe hypoglycemia	One episode of severe hypoglycemia defined as low blood glucose with mental status impairment severe enough to require third-party assistance
Dizziness/hypotension	Orthostatic CNS symptoms (dizziness, confusion) that are not vasovagal responses to provocative stimuli (for example, phlebotomy, nausea, bowel or bladder function), and are associated with orthostatic SBP decrease >20 mm Hg or DBP decrease >10 mm Hg or heart rate >105 bpm, for >3 hours
Sensorium	Disorientation to time, place, or identity. Any abnormal ideation
Mood	Feelings of grief or loss that interfere with study procedures or activities of daily living; any suicidal ideation
Headache/pain	Any focal or generalized head pain that disrupts normal activities and is not responsive to medical therapies
Pruritus	Generalized itching for more than 24 hours that is unresponsive to oral antihistamine
Signs	
Systolic blood pressure	>30 mm Hg increase from baseline values and an absolute level >190 mm Hg
Diastolic blood pressure	>20 mm Hg increase from baseline values and an absolute level >115 mm Hg
Heart rate	Resting (sitting or recumbent) HR >120 bpm
Cardiac rhythm	Any rhythm other than sinus rhythm, mild sinus bradycardia, or mild sinus tachycardia
QTc	>500 milliseconds or >60 milliseconds increase from baseline value
QRS morphology	Significant prolongation of QRS interval or new onset of bundle branch block
Tremor	Readily visible tremor during normal movement deemed unrelated to hypoglycemia
Reflexes	New onset of clonic reflexes
Clinical Laboratory	Confirmed by repeat measurements within 48 hours
Hemoglobin	Absolute value <10 g/dL and >2 g/dL reduction from baseline
Neutropenia	Absolute neutrophils <1,500/ μ L and >1,000 μ L decrease from baseline

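### Stopping rule 4, the only mandatory rule that can count GI tolerability events, names only moderate AEs and, read literally, misses AEs that are severe from onset

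*Protocol*

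**What the plan says.** Protocol Section 7.4.1 lists five scenarios. If any one occurs, "dosing at the current level and dose-escalation from Cohort 1 to Cohort 2 will be discontinued".

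- **Rule 1** is met by one patient with "an SAE other than anticipated pharmacology of LY3298176 (for example, GI-related AEs [particularly nausea, vomiting, and diarrhea] or hypoglycemia".
- **Rule 2** is met by two clinically significant events (CSEs) in a cohort "that are related to LY3298176 administration, with the exception of anticipated pharmacology of LY3298176".
- **Rule 3** counts only symptomatic hypoglycemia at or below 54 mg/dL, in at least half of a cohort.
- **Rule 4** reads "if more than 4 patients in 1 cohort experience moderate treatment-related AEs that impair normal activities". It has no exemption for anticipated pharmacology.
- **Rule 5** counts only acute pancreatitis, in two or more patients.

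The text available to us does not define the AE severity grades, and neither document extends rule 4 beyond the moderate grade.

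**The concern.** Section 5.5 names GI events as the expected dose-limiting problem and reports that 15 mg reached by rapid titration was poorly tolerated. Section 3.2 adds that two healthy subjects given a single 8 mg dose in Study GPGA needed antiemetics and intravenous fluids, and that escalation there was stopped. GI intolerability is therefore the event that the stopping list most needs to catch, and only rule 4 can catch it.

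As worded, rule 4 counts a patient whose vomiting is moderate but not one whose vomiting is severe from the start. The rule becomes harder to meet as the events become worse. This is the first study of the drug in Japanese subjects, it runs at multiple sites, and down-titration is not allowed, so the mandatory part of the stopping list should not depend on how each reader interprets one adjective.

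**Working it through.** **1. Which rules can count a GI tolerability event?** The plan states no operating characteristic for rule 4, so there is no figure to reproduce. The five rules can be compared directly.

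| Rule | Counts nausea, vomiting or diarrhea? |
|---|---|
| 1 (SAE) | No: exempt as anticipated pharmacology, even if serious |
| 2 (CSE) | No: same exemption |
| 3 | No: hypoglycemia only |
| 4 | Yes, if moderate, related and activity-impairing |
| 5 | No: acute pancreatitis only |

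**2. Does the protocol elsewhere use a single grade to mean that grade or worse?** In the two places set beside rule 4 it writes the range out. Section 9.6.4 refers to "an association of the TE-ADA with a moderate to severe injection-site reaction or infusion-related reaction", and Appendix 4 aims to "define a level of moderate to severe abnormality in safety findings that could cause harm to health". Rule 4 has no such range.

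**3. Counts under each wording.** Let M be the number of patients with at least one moderate, related, activity-impairing AE. Let S be the number whose only such AEs are severe from onset. More than 4 patients means 5 or more.

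- Literal rule: met if M ≥ 5.
- With *or severe* added: met if M + S ≥ 5.

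The denominators are patients on LY3298176, 12 in Cohort 1 and 16 in Cohort 2 (Section 10.1), because Section 7.4.1 lists events after placebo among its examples of unrelated events.

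| Case | M | S | Affected (M + S) | Literal rule | Amended rule |
|---|---|---|---|---|---|
| Cohort 1, all moderate | 5 | 0 | 5 of 12 | met (5) | met (5) |
| Cohort 1, one patient worse | 4 | 1 | 5 of 12 | not met (4) | met (5) |
| Cohort 1, upper bound | 4 | 12 − 4 = 8 | 12 of 12 | not met (4) | met (12) |
| Cohort 2, upper bound | 4 | 16 − 4 = 12 | 16 of 16 | not met (4) | met (16) |

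The second row is the one that matters in practice: grading one patient severe rather than moderate changes the result.

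**4. Patients who still count.** An AE that worsens from moderate to severe has been moderate, so it counts. SAP Section 9.5.1 keeps each severity in the listings, although its summary tables keep only the worst. A patient with a severe AE and a separate moderate one also counts. The gap is confined to severe-only patients.

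**5. Illustration with assumed rates.** Neither rate below is in the documents. Let p be the share of treated patients with a related, activity-impairing AE of at least moderate grade, and s the share of those who are severe-only. With independent patients and n = 12, the chance of meeting the rule is P(X ≥ 5), where X is Binomial(12, p) for the amended rule and Binomial(12, p(1 − s)) for the literal rule.

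| p | Amended | Literal, s = 0.1 | Literal, s = 0.2 | Literal, s = 0.3 |
|---|---|---|---|---|
| 0.4 | 0.56 | 0.45 | 0.33 | 0.23 |
| 0.5 | 0.81 | 0.70 | 0.56 | 0.42 |
| 0.6 | 0.94 | 0.87 | 0.77 | 0.62 |

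**The case against.** The strongest reply is that nobody would read the rule this way. A severe AE impairs normal activities even more than a moderate one, so an investigator and sponsor acting sensibly would count it. The two comparison texts deal with antibody follow-up and a CSE guideline, and do not establish a drafting convention for Section 7.4.1. That stands as a statement of probable intent. It does not supply the missing words, and without defined grades the reader has to infer them.

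The second reply is that other safeguards exist:

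- Section 5.1 requires a review of the staggered group, after which "if no relevant safety signals are noted, the remaining patients will be dosed".
- Section 7.4.1 says "No dose decision can occur without prior discussion and agreement between the investigator and the Lilly clinical pharmacologist, CRP, or CRS", and it allows an 8 mg regimen in Cohort 2 if 10 mg is poorly tolerated.
- Section 7.4 lets the investigator withhold up-titration, and Section 9.4.4 has the sponsor review GI events periodically.
- Section 9.4.4.2 stops LY3298176 in any patient with symptoms of pancreatitis. Under Appendix 6 these may include severe nausea and vomiting with other consistent symptoms.
- Consequences listed in Appendix 4, such as a creatinine rise or orthostatic symptoms, could arguably count under rule 2.

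These lower the risk of harm. However, they rest on judgement, apply to one patient at a time, or need a separate finding, and none makes rule 4 count a severe-only GI event.

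Third, the upper-bound cases are unlikely, and the escalation review may include as few as five treated patients, all of whom would have to be affected for rule 4 to be met. Both points are fair. But with exactly five treated patients, one severe-only patient leaves at most 5 − 1 = 4 who can count, so the literal rule could not be met at all.

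**Conclusion.** The concern holds. Rule 4 is the only mandatory rule that can count GI tolerability events, and as written it omits those that are severe from onset. One patient graded severe instead of moderate is enough to turn a stop into no stop (4 + 1 against 5 + 0). The upper bounds are 12 of 12 patients affected in Cohort 1 and 16 of 16 in Cohort 2 without the rule being met.

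The counts assume no event rates. They rest on the literal wording and on counting patients on LY3298176 only. The probabilities in the illustration depend entirely on the assumed p and s.

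This is a drafting gap that the discretionary reviews partly cover, and it was probably unintended. It should still be corrected, because it sits in the one mandatory rule for the expected dose-limiting toxicity.

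**What to change.** In rule 4 of Protocol Section 7.4.1, insert *or severe* after *moderate*. All four cases in the count table then meet the rule.

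The cost is two words. Severity is already recorded for nausea and vomiting events (Section 9.4.4.5), and symptom incidence is already presented by severity (Section 10.3.1.1), so no new data are needed.

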7.5. Preparation/Handling/Storage/Accountability

The investigator or designee must confirm appropriate temperature conditions (2°C to 8°C) have been maintained, as communicated by sponsor, during transit for all IMP received and any discrepancies are reported and resolved before use of the IMP.

Only participants enrolled in the study may receive IMP or study materials, and only authorized site staff may supply or administer IMP. All IMP should be stored in an environmentally controlled and monitored (manual or automated) area in accordance with the labeled storage conditions with access limited to the investigator and authorized site staff.

The investigator, institution, or the head of the medical institution (where applicable) is responsible for IMP accountability, reconciliation, and record maintenance (such as receipt, reconciliation, and final disposition records).

7.6. Treatment Compliance

The IMP will be administered at the clinical site, and documentation of treatment administration will occur at the CRU.

7.7. Concomitant Therapy

Treatment with drugs that are excluded in the entry criteria ([Section 6](#)) is not permitted.

Patients on stable concomitant medication at the time of study entry should continue their regular, unchanged dose throughout the study.

In general, concomitant medication should be avoided; however, acetaminophen (1g/dose, maximum 2g/day) may be administered at the discretion of the investigator for treatment of headaches, etc. If the need for concomitant medication (other than acetaminophen) arises, inclusion or continuation of the patient may be at the discretion of the investigator, preferably after consultation with a Lilly clinical pharmacologist, CRP, or CRS. Stable doses (refer to

Section 6) of over-the-counter or prescription medications (for example, antihypertensive agents, aspirin, lipid-lowering agents) for treatment of concurrent medical conditions are allowed.

All concomitant medications used during the course of study will be recorded in the eCRF.

7.8. Treatment after the End of the Study

Not applicable for this study.

8. Discontinuation Criteria

Patients discontinuing from the treatment prematurely for any reason should complete AE and other follow-up procedures per Section 2 of this protocol.

8.1. Discontinuation from Study Treatment

Discontinuation of the IMP for abnormal pancreatic tests **should be considered** by the investigator when a patient meets the following condition:

- lipase and/or amylase are confirmed to be $\geq 3 \times$ ULN. Please refer to algorithm for the monitoring of pancreatic events in [Appendix 6](#).

Discontinuation of the IMP for abnormal liver tests **should be considered** by the investigator when a patient meets 1 of the following conditions after consultation with the Lilly-designated medical monitor:

- ALT or AST $>8 \times$ ULN
- ALT or AST $>5 \times$ ULN sustained for more than 2 weeks
- ALT or AST $>3 \times$ ULN and TBL $>2 \times$ ULN or international normalized ratio >1.5
- ALT or AST $>3 \times$ ULN with the appearance of fatigue, nausea, vomiting, right upper-quadrant pain or tenderness, fever, rash, and/or eosinophilia ($>5\%$)
- alkaline phosphatase (ALP) $>3 \times$ ULN
- ALP $>2.5 \times$ ULN and TBL $>2 \times$ ULN
- ALP $>2.5 \times$ ULN with the appearance of fatigue, nausea, vomiting, right quadrant pain or tenderness, fever, rash, and/or eosinophilia ($>5\%$)

8.1.1. Discontinuation of Inadvertently Enrolled Patients

If the sponsor or investigator identifies a patient who did not meet enrollment criteria and was inadvertently enrolled, a discussion must occur between the Lilly clinical pharmacologist, CRP, or CRS and the investigator to determine if the patient may continue in the study. If both agree it is medically appropriate to continue, the investigator must obtain documented approval from the Lilly clinical pharmacologist, CRP, or CRS to allow the inadvertently enrolled patient to continue in the study with or without continued treatment with IMP.

8.2. Discontinuation from the Study

Patients will be discontinued in the following circumstances:

- enrollment in any other clinical study involving an IMP or enrollment in any other type of medical research judged not to be scientifically or medically compatible with this study
- participation in the study needs to be stopped for medical, safety, regulatory, or other reasons consistent with applicable laws, regulations, and good clinical practice
- investigator decision

- the investigator decides that the patient should be discontinued from the study
- if the patient, for any reason, requires treatment with another therapeutic agent that has been demonstrated to be effective for treatment of the study indication, then discontinuation from the study occurs before introduction of the new agent
- patient decision
 - the patient or legal representative requests to be withdrawn from the study

8.3. Patients Lost to Follow-up

A patient will be considered lost to follow-up if he or she repeatedly fails to return for scheduled visits and is unable to be contacted by the study site. Site personnel are expected to make diligent attempts to contact patients who fail to return for a scheduled visit or were otherwise unable to be followed up by the site.

9. Study Assessments and Procedures

Section 2 lists the Schedule of Activities, detailing the study procedures and their timing (including tolerance limits for timing).

[Appendix 2](#) lists the clinical laboratory tests that will be performed for this study.

[Appendix 7](#) provides a summary of the maximum number and volume of invasive blood samples, for all sampling, during the study.

Unless otherwise stated in subsections below, all samples collected for specified laboratory tests will be destroyed within 60 days of receipt of confirmed test results. Certain samples may be retained for a longer period, if necessary, to comply with applicable laws, regulations, or laboratory certification standards.

9.1. Efficacy Assessments

This section is not applicable for this study.

9.2. Adverse Events

Investigators are responsible for monitoring the safety of patients who have entered this study and for alerting Lilly or its designee to any event that seems unusual, even if this event may be considered an unanticipated benefit to the patient.

The investigator is responsible for the appropriate medical care of patients during the study.

Investigators must document their review of each laboratory safety report.

The investigator remains responsible for following, through an appropriate health care option, AEs that are serious or otherwise medically important, considered related to the IMP or the study, or that caused the patient to discontinue the IMP before completing the study. The patient should be followed up until the event resolves, stabilizes with appropriate diagnostic evaluation, or is reasonably explained. The frequency of follow-up evaluations of the AE is left to the discretion of the investigator.

After the informed consent form is signed, study site personnel will record, via eCRF, the occurrence and nature of each patient's preexisting conditions, including clinically significant signs and symptoms of the disease under treatment in the study. Additionally, site personnel will record any change in the condition(s) and the occurrence and nature of any AEs.

The investigator will interpret and document whether or not an AE has a reasonable possibility of being related to study treatment or a study procedure, taking into account the disease, concomitant treatment, or pathologies.

A "reasonable possibility" means that there is a potential cause and effect relationship between the IMP, study device, and/or study procedure and the AE.

Planned surgeries should not be reported as AEs unless the underlying medical condition has worsened during the course of the study.

If a patient's IMP is discontinued as a result of an AE, study site personnel must report this to Lilly or its designee via eCRF.

